## 5.2 Primary Endpoint: TLF at 12 Months

### 5.2.1 Primary Analysis

The primary analysis will be a test for non-inferiority of the BuMA DES compared with DP EES for the primary endpoint of TLF at 12 months, performed in the Per Protocol (PP) and Intention to Treat (ITT) populations using the Farrington-Manning test (non-inferiority margin = 3.575%, one-sided alpha = 0.025).

If the upper bound of the two-sided 95% confidence interval (one-sided 97.5% CI) for the risk difference (BuMA DES – DP EES) is less than the non-inferiority margin of 3.575%, then non-inferiority will have been met and a formal superiority test will be performed for the powered secondary endpoint. If superiority for the powered secondary endpoint is met, formal superiority testing will be performed for

	FORM	Document No: BIO-TMP-0702 Revision: 00
	TITLE Statistical Analysis Plan	Effective date: 16-Mar-2018 Department: BIO

the primary endpoint at alpha = 0.05 (two-sided) and superiority will be declared if the upper bound of the two-sided 95% confidence interval for the risk difference (BuMA DES – DP EES) is less than 0%.

For the primary analysis, only subjects who experienced a primary endpoint event within 12 months (365 days) from randomization or who had at least 11 months follow-up (1 year minus the allowable 30 day window) and who meet the applicable analysis population definition will be included in the analysis. Analysis is at the subject level. A subject will be considered a failure for TLF if the subject experiences a cardiac death, a target vessel-related myocardial infarction (TV-MI) in any target vessel, or clinically-driven target lesion revascularization (TLR) in any study target lesion.

### 5.2.2 Sensitivity/Robustness Analyses

A sensitivity analysis of the primary safety and efficacy endpoint will be performed on the Modified Per-Protocol (MPP) population. In addition, to support the interpretation of the primary analysis, a tipping point analysis will be performed as a sensitivity analysis. Tipping point analysis involves performing the primary analysis of TLF at 12 months repeatedly for every possible scenario involving the missing outcome data. That is, we will calculate the non-inferiority p-value from the Farrington-Manning test for all possible outcome combinations (event vs no event) for the BuMA DES and DP EES arms.

In addition to tipping point analysis, a sensitivity analysis for the primary endpoint will also be conducted according to the pre-specified alternate biomarker thresholds for PCI-related MIs (see Section 2.2.3.3 for primary MI definition). The alternate thresholds for cTn to be used in the sensitivity analyses are: 3, 10, 35, and 70 x 99th percentile URL.

## 5.3 Secondary Endpoints

### 5.3.1 Secondary Powered Endpoint

The powered secondary endpoint of long-term safety and efficacy, defined as TLF between 12 months and 5 years by landmark Kaplan-Meier analysis, will be a test for superiority of the BuMA DES group to the DP EES group via the log-rank test in the ITT population. Subjects who experience TLF prior to 12 months will be excluded from this analysis. The analysis will be performed when the last enrolled subject has completed his/her 5-year clinical follow-up visit, and will be performed only if non-inferiority for the primary endpoint has been met.

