### 11.1.2 Secondary Powered Endpoint Hypothesis

If the primary non-inferiority hypothesis is confirmed, the secondary powered endpoint hypothesis will be tested. The secondary powered endpoint hypothesis is that the rate of TLF in the treatment group is superior to the rate of TLF in the control group over the period between 1 and 5 years postprocedure in a landmark analysis. Specifically, the null and alternative hypotheses are:

$$H_0: S_I(t) = S_C(t) \text{ for all } t$$

$$H_A: S_I(t) \neq S_C(t)$$

Where:

$S_I(t)$  = the survival distribution in the Intervention group and  $S_C(t)$  = the survival distribution in the Control group

Superiority will be demonstrated if the survival distributions are not equal using the log-rank test in the Intention to Treat patient population.

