### 11.4.4 Secondary Powered Endpoint Analysis

The powered secondary endpoint of long-term safety and efficacy, defined as TLF between 12 months and 5 years by landmark Kaplan-Meier analysis, will be a test for superiority of the BuMA DES group to the DP EES group via the log-rank test in the ITT population. Subjects who experience TLF prior to 12 months will be excluded from this analysis. The analysis will be performed when the last enrolled subject has completed his/her 5 year clinical follow-up visit, and will be performed only if non-inferiority for the primary endpoint has been met.

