## 11.5 Measures to Minimize Bias

### 11.5.1 Randomization

Subjects will be randomly assigned to a treatment group in a 2:1 ratio (BuMA DES : DP EES) after eligibility criteria have been confirmed (at the time of the index procedure). Randomization will be stratified by presentation (acute coronary syndrome vs. non-ACS) and diabetes status (subjects with vs. without medically-treated diabetes mellitus) given the influence of clinical presentation and diabetes status on the outcome of subjects with CAD. Randomization will also be stratified by study site to avoid introducing bias as a result of site-specific factors.

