#### **1.2.1.2 Secondary Powered Endpoint Hypothesis**

If the primary non-inferiority hypothesis is confirmed, the secondary powered endpoint hypothesis will be tested. The secondary powered endpoint hypothesis is that the rate of TLF in the treatment group is superior to the rate of TLF in the control group over the period between 1 and 5 years post-procedure in a landmark analysis. Specifically, the null and alternative hypotheses are:

$$H_0: S_I(t) = S_C(t) \text{ for all } t$$

$$H_A: S_I(t) \neq S_C(t)$$

Where:

$S_I(t)$  = the survival distribution in the Intervention group and  $S_C(t)$  = the survival distribution in the Control group

Superiority will be demonstrated if the survival distributions are not equal using the log-rank test in the Intention to Treat patient population.

Clinical endpoint data will be adjudicated by an independent Clinical Event Committee, and an independent Data Safety Monitoring Committee will monitor the safety of subjects throughout the trial. Index procedure and event-driven angiographic data will be analyzed by an independent Angiographic Core Laboratory.

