#### 4.1.2 Sample Size - Secondary Powered Endpoint

The powered secondary endpoint of the trial is long-term safety and efficacy, defined as TLF between 12 months and 5 years by landmark analysis. The analysis will be performed when the last enrolled subject has completed his/her 5 year clinical follow-up visit.

We assume:

- Randomization ratio is 2:1 (BuMA DES: DP EES)
- The landmark (between 12 months and 5 years) TLF rate in the Control group = 8%
- The rate of TLF in the control group at 12 months = 6.5%
- A constant Hazard Ratio in the Intervention group compared to the Control Group = 0.52
- Loss to follow-up = 5% per year (a standard assumption for contemporary trials of coronary stents)
- $\alpha = 0.05$  (two-sided)

Given these assumptions, the planned study sample size of 1444 evaluable subjects at 1 year (accounting for an estimated 5% loss to follow-up at 1 year, a 6.5% rate of TLF prior to 1 year, and a continued annual loss to follow-up of 5%) will provide approximately 80% power to demonstrate superiority of the BuMA DES to DP EES using the log-rank test.

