#### 4.3 General Methods

All data collected will be summarized overall and by treatment. Descriptive statistics of continuous variables will include mean, standard deviation, median, quartiles, range, and sample size. Differences between the treatment arms, where specified, will be summarized with the differences of the two means, 95% confidence intervals for the difference between the means, and p-values based on a t-test. The distributions within each group will be tested for normality using the Shapiro-Wilks test and if normality cannot be assumed then a Wilcoxon rank-sum test for medians will be performed. The confidence interval for the difference of two means will be calculated under the assumption of unequal variances.

For categorical variables, descriptive statistics will include count, percentage, and sample size. Categorical data will be presented as n/N (%), and percentages will be rounded and reported to a single decimal point (xx.x %). Unless otherwise noted, subjects with missing data will be excluded from the denominator. Differences between the two treatment arms, where specified, will be summarized with the difference in percentages, the asymptotic 95% confidence interval for the difference of two percentages, and a p-value based on a chi-squared test. If 20% or more of the expected cell frequencies are less than 5 then a Fisher's Exact Test will be used to test for differences in proportions.

Survival analysis techniques will be used to analyze the time-to-event variables that occur at or after 30 days of follow-up. Time to event analysis will be performed for each time point separately (i.e. up to 30 days, 6-months (180 days), 1 year (365 days), 2 years (730 days), 3 years (1095 days), 4 years (1460 days), and 5 years (1825 days)) and summarized using the Kaplan-Meier estimated event rates and number of events. The log-rank test will be used for comparing treatments. Hazard ratios and the associated two sided confidence intervals (Wald's CI) will be estimated by Cox proportional hazards model, including treatment as a covariate.

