### 5.3.3 Secondary Safety Endpoints

All secondary safety endpoints will be evaluated in the ITT analysis population. No formal hypothesis testing will be performed.

Descriptive statistics for in-hospital events will include count, percentage, and sample size. Subjects with missing data will be excluded from the denominator. Differences in event rates between the two treatment arms will be summarized descriptively with the difference in percentages, the asymptotic 95% confidence interval for the difference of two percentages, and a p-value based on a chi-squared test. If 20% or more of the expected cell frequencies are less than 5 then a Fisher's Exact Test will be used to test for differences in proportions.

	FORM	Document No: BIO-TMP-0702 Revision: 00
	TITLE Statistical Analysis Plan	Effective date: 16-Mar-2018 Department: BIO

Survival analysis techniques, as detailed in Section 4.3, will be used to analyze all secondary safety endpoints at 30 days, 6 months, and 1, 2, 3, 4, and 5 years. Summary statistics will include Kaplan-Meier estimated event rates and number of events. The log-rank test will be used for comparing treatments. Hazard ratios and the associated two-sided confidence intervals (Wald's CI) will be estimated by Cox proportional hazards model, including treatment as a covariate.

A secondary analysis of all secondary safety endpoints will also be performed in the PP analysis population.

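### Free improvement, not an error: the confirmatory landmark log-rank test does not use the presentation and diabetes strata of the randomisation

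*SAP*

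**What the plan says.** Protocol 11.5.1 stratifies the 2:1 randomisation by presentation and by medically-treated diabetes, "given the influence of clinical presentation and diabetes status on the outcome of subjects with CAD". Site is a third stratification factor.

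For the powered secondary endpoint, four sections name the test and none names strata:
- SAP 5.3.1: it "will be a test for superiority of the BuMA DES group to the DP EES group via the log-rank test in the ITT population".
- SAP 1.2.1.2: "Superiority will be demonstrated if the survival distributions are not equal using the log-rank test in the Intention to Treat patient population".
- Protocol 11.1.2: "using the log-rank test in the Intention to Treat patient population".
- Protocol 11.4.4: "via the log-rank test in the ITT population".

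SAP 4.1.2 says that 1444 evaluable subjects at 1 year "will provide approximately 80% power to demonstrate superiority of the BuMA DES to DP EES using the log-rank test". SAP 5.3.1 names no hazard ratio. The general rule in SAP 4.3 is that hazard ratios "will be estimated by Cox proportional hazards model, including treatment as a covariate".

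Presentation and diabetes otherwise appear only as subgroups. SAP 5.4 reports the primary and landmark endpoints within their levels, with interaction p-values for description. The only stratified analysis in the SAP (5.5) is by site, for the primary endpoint, if site heterogeneity is found.

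**The concern.** If two factors are important enough to stratify the randomisation because they affect outcome, the usual practice is to carry them into the confirmatory test. Ignoring prognostic strata makes a log-rank test slightly conservative and pulls a crude hazard ratio slightly towards 1.

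The landmark test is where this could count. It is the only superiority hypothesis with a stated power, it rests on few events, and under SAP 4.1.3 it also gates the formal superiority test of the primary endpoint. At stake is a small amount of power that the recorded strata could supply at no cost in patients.

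**Working it through.** **Inputs from the documents** (SAP 4.1.2, Protocol 11.3.2): 1632 randomised 2:1; 5% loss and 6.5% TLF in year 1; control TLF of 8% between 12 months and 5 years; constant hazard ratio 0.52; 5% loss per year; two-sided alpha 0.05.

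**The plan's own figures first.**
- Subjects at the landmark: 1632 × (1 − 0.05 − 0.065) = 1444.3, matching 1444.
- Hazards per year: control −ln(0.92)/4 = 0.02085; BuMA DES 0.52 × 0.02085 = 0.01084; loss −ln(0.95) = 0.05129.
- Event probability over 4 years, λ/(λ+loss) × [1 − exp(−4(λ+loss))]: control 0.0724, BuMA DES 0.0384.
- Events: 1444/3 × 0.0724 = 34.9 and 1444 × 2/3 × 0.0384 = 37.0, about 72 in total.
- Freedman's formula for 2:1: √(2 × 71.8) × 0.48/2.04 − 1.96 = 0.86, power 80.5%.
- Lachin-Foulkes: 78.1%. Simulation of the unstratified log-rank test: about 78.5%.
- Schoenfeld's formula is lower, at 74.3%, but simulation supports the stated value to within 2 points.

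**Assumptions, not in the documents:** 50% ACS, 30% diabetes; a risk ratio of 1, 1.5, 2 or 3 for each factor; permuted blocks of 3 or 6 within 130 unequal sites × 4 cells.

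**Power, 100,000 simulated trials per scenario:**

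| Risk ratio per factor | Blocks of 3: unstratified → four cells | Gain (points) | Blocks of 6: unstratified → four cells | Gain (points) |
|---|---|---|---|---|
| 1 | 0.785 → 0.784 | −0.05 | 0.787 → 0.787 | −0.02 |
| 1.5 | 0.786 → 0.787 | +0.1 | 0.786 → 0.787 | +0.05 |
| 2 | 0.781 → 0.784 | +0.3 | 0.782 → 0.786 | +0.4 |
| 3 | 0.778 → 0.790 | +1.2 | 0.774 → 0.788 | +1.3 |

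Gains are taken before rounding; their paired standard error is 0.03 to 0.06 points.

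With 30% ACS and 20% diabetes, or 70% and 40% (blocks of 3), the gains are +0.1 at 1.5, +0.3 to +0.4 at 2, and +1.0 to +1.2 at 3. A simpler simulation without sites (20,000 runs) agrees: 78.7% → 78.7% with no prognostic effect, and 78.0% → 78.9% with ratios of 2 for ACS and 3 for diabetes.

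**Type I error:** unstratified 0.048 to 0.051, stratified 0.049 to 0.051 (Monte Carlo standard error 0.0007). Both hold 5%.

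**Hazard ratio:** a within-stratum value of 0.52 appears without strata as 0.521, 0.522 and 0.527 at risk ratios 1.5, 2 and 3.

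**The largest gain in events:** events needed = (1.96 + z)²/[(2/9) × (ln 0.52)²], where z is the normal quantile of the power and the denominator is 0.0950. Power 78.5% needs 79.5 events and 79.8% needs 82.2, a rise of 3.3%. Applied to the trial's own 72 events, that is about 2.4.

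**The case against.** The strongest case against is that this is preference. The documents name the log-rank test consistently, the power was calculated for that test, and it is valid. A gain of about a point needs a risk ratio of 3 for both factors. With an 8% overall control rate, four-year rates would then run from about 2.6% in the lowest-risk cell to 21.4% in the highest, and nothing in the documents supports that spread. Protocol 11.5.1 says that the factors matter but gives no size, and says nothing specific to TLF after 12 months among subjects still free of it. Balance on both factors already comes from the randomisation, and SAP 5.4 shows landmark results by each. Changing a test named in the protocol also means paperwork.

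The point about size stands: the gain is usually under half a point. So does the point about paperwork, so the change is free only in patients and data. Neither defeats a change whose worst simulated result is a loss of 0.05 points.

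Stronger readings are tempting. A reader might infer that stratified randomisation makes the unstratified test invalid or leaves the trial underpowered; the type I error and the reproduced power show otherwise. A reader might infer that the SAP commits to a crude landmark hazard ratio. SAP 5.3.1 names none, and SAP 4.3 is a general rule for analyses timed from randomisation. A reader might also extend the point to the other secondary endpoints, but these are descriptive: "No formal hypothesis testing will be performed" (SAP 5.3.3, for the safety endpoints).

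**Conclusion.** The point holds as an optional improvement. The landmark test is valid and its power statement is sound. It leaves unused two strata that the protocol itself calls influential. Stratifying by the four cells is worth about zero if the factors are not prognostic, less than half a point of power at risk ratios up to 2 per factor, and about one point, or about 2.4 events, only if both are 3. These sizes rest on assumed prevalences and risk ratios; varying the prevalences changed them little. Nothing here calls for a change to the sample size, alpha, margin or primary endpoint.

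**What to change.** In SAP 5.3.1, with matching words in SAP 1.2.1.2 and Protocol 11.1.2 and 11.4.4, specify:
- a two-sided log-rank test in the ITT population, stratified by the four cells of presentation (ACS, non-ACS) by medically-treated diabetes (yes, no), as declared at randomisation;
- strata not crossed with site;
- as supportive analyses, the unstratified log-rank test and the stratified test with corrected strata;
- if a hazard ratio is reported for the landmark period, a Cox model with treatment, stratified by the same four cells and labelled as a within-stratum hazard ratio. Kaplan-Meier curves stay unstratified.

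The site clause is a guard on the new wording only. Neither document proposes crossing with site for this endpoint, but a loose reference to the randomisation strata would include it. In the scenarios tabulated above, crossing cut power by between 7.2 points (0.785 to 0.713) and 10.6 points (0.774 to 0.668). The corrected-strata check is sensible because SAP 3.3 provides for subjects whose stratum was wrongly declared.

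Cost: no patients, visits or data, and one strata statement in the program. The change must be recorded in a protocol amendment or the clinical study report, as SAP 1.0 requires. If it is judged substantive, the approvals in Protocol 15.2 and 15.7 come first. It should be fixed before the 12-month unblinding (Protocol 11.5.2), so that the choice cannot depend on the data. The primary Farrington-Manning and tipping-point analyses, the sample size statement and the descriptive Cox models stay as they are.

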### 5.3.2 Secondary Efficacy Endpoints

Lesion Success will be assessed on a lesion level, performed on the ITT analysis population, and presented for overall subjects and by treatment arm. The analysis of Device Success will include all

	FORM	Document No BIO-TMP-0702 Revision: 00
	TITLE Statistical Analysis Plan	Effective date: 16-Mar-2018 Department: BIO

target lesions in which the assigned device is attempted in the denominator [1]. As a secondary analysis, the device success analysis will include all target lesions in the denominator, whether or not an attempt to implant the assigned device was made.

No formal hypothesis testing will be performed. Both endpoints will be compared descriptively between the treatment arms using a generalized linear mixed model that accounts for the clustering effect of multiple lesions per subject. The model includes treatment as a fixed effect and subject as a random effect. Two sided 95% CI for the estimated difference and p-values will be reported.

Procedural success and in- hospital TVR, TLR, TVF, and TLF events will be evaluated in the ITT analysis population. No formal hypothesis testing will be performed. Descriptive statistics will include count, percentage, and sample size. Subjects with missing data will be excluded from the denominator. Differences between the two treatment arms will be summarized descriptively with the difference in percentages, the asymptotic 95% confidence interval for the difference of two percentages, and a p-value based on a chi-squared test. If 20% or more of the expected cell frequencies are less than 5 then a Fisher's Exact Test will be used to test for differences in proportions.

Survival analysis techniques, as detailed in Section 4.3, will be used to analyze the TVR, TLR, TVF, and TLF events at 30 days, 6 months, and 1, 2, 3, 4, and 5 years. Summary statistics will include Kaplan-Meier estimated event rates and number of events. The log-rank test will be used for comparing treatments. Hazard ratios and the associated two-sided confidence intervals (Wald's CI) will be estimated by Cox proportional hazards model, including treatment as a covariate.

A secondary analysis of all secondary efficacy endpoints will also be performed in the PP analysis population.

### 5.3.3 Secondary Safety Endpoints

All secondary safety endpoints will be evaluated in the ITT analysis population. No formal hypothesis testing will be performed.

Descriptive statistics for in-hospital events will include count, percentage, and sample size. Subjects with missing data will be excluded from the denominator. Differences in event rates between the two treatment arms will be summarized descriptively with the difference in percentages, the asymptotic 95% confidence interval for the difference of two percentages, and a p-value based on a chi-squared test. If 20% or more of the expected cell frequencies are less than 5 then a Fisher's Exact Test will be used to test for differences in proportions.

	FORM	Document No: BIO-TMP-0702 Revision: 00
	TITLE Statistical Analysis Plan	Effective date: 16-Mar-2018 Department: BIO

Survival analysis techniques, as detailed in Section 4.3, will be used to analyze all secondary safety endpoints at 30 days, 6 months, and 1, 2, 3, 4, and 5 years. Summary statistics will include Kaplan-Meier estimated event rates and number of events. The log-rank test will be used for comparing treatments. Hazard ratios and the associated two-sided confidence intervals (Wald's CI) will be estimated by Cox proportional hazards model, including treatment as a covariate.

A secondary analysis of all secondary safety endpoints will also be performed in the PP analysis population.

#### 5.4 Subgroup Analyses

All Subgroup analyses will be performed for the primary and powered secondary endpoint in their respective primary analysis populations for the following subgroups, and results will be reported by treatment group using descriptive statistics:

- Enrollment region (North America vs. Japan vs. Europe)
- Presentation (stable coronary artery disease vs. acute coronary syndromes)
- Single- versus multi-vessel disease (1 vs. 2 target vessels)
- Diabetes status (subjects with vs. without medically-treated diabetes mellitus)
- Subject sex (male vs. female)

No formal hypothesis testing for subgroup analyses will be performed. For the primary endpoint, a descriptive assessment of the effect of subgroup on the primary endpoint will be carried out in the PP and ITT populations using interaction testing for subgroup by treatment effect from a logistic regression model with a 0.15 level of significance. For the powered secondary endpoint, the interaction p-value from a Cox proportional hazards model with treatment, subgroup, and treatment by subgroup interaction terms as covariates will be presented for descriptive purposes only.

